7.1.2 Follow up assessments

For study participants in MF groups (MF + ICB and MF+SOC), follow up assessments to evaluate primary and secondary outcomes will be conducted in the field at 9- and 18- months. During follow up assessments, MF group participants will:

- Provide a blood draw for HIV viral load testing (study month 18 only)
- Provide a systolic blood pressure reading (study month 18 only)
- Provide an HbA1c point of care test, if clinically indicated (study month 18 only)
- Complete the survey assessments (study month 9 and 18)

Trained research assistants will work with the clinical teams to collect survey assessment data on mobile tablets. Clinical teams will record blood pressure and HbA1c results in the patient's medical records and in the study REDCap records. At 18 months, clinical officers and research assistants will transport blood samples from the community to the Eldoret reference lab for analysis. For participants who do not attend MF group meetings during assessment time points (months 9 and 18), research assistants will use participant's contact information to schedule follow-up meetings to collect data if participants are willing to meet outside of the regularly scheduled MF meeting time. We will access and review AMRS for data on secondary outcomes (i.e., retention in care and chronic disease composite score).

For study participants receiving SOC (Study Arm C), follow up assessments to evaluate primary and secondary outcomes will be conducted at AMPATH facilities when the patient returns for their HIV clinic visit at 18-months. During follow up assessments, SOC patients will:

- Provide a blood draw for HIV viral load testing
- Complete the survey assessments

7.1.3 Fidelity monitoring

During the first six months of the study, intervention staff will meet weekly to review study progress, care protocols, and any issues that have arisen during the ICB care delivery activities. Following the initial six months, the project manager will visit 4 randomly selected intervention groups (MF+ICB) monthly to monitor activities and ensure that procedures for care delivery are being followed. Using a checklist for adherence to study protocol, the project manager will rate each session. Staff in groups with low ratings will be retrained and monitored for the following 3 months. During the random audit, any staff member found in violation of study protocol will be suspended and retrained.

7.2 Statistical analysis ⁶

The primary analysis of interest is comparing viral suppression at 18 months between the MF+ICB (Study Arm A) and MF+SOC groups (Study Arm B). As a secondary hypothesis, we will test MF+ICB vs SOC alone and MF+SOC vs SOC alone. To test both the primary and the secondary hypotheses we will use a generalized mixed effects model.³³ For the primary outcome, the model we will use is

$$log(P(Y_{ij}=1|I_j,S_j,VB_{ij},c_j)) = \beta_0 + \beta_1 I_j + \beta_2 S_j + \beta_3 VB_{ij} + c_j$$

⁶ See the Addendum to the overall project protocol starting on page 100 for changes made to the statistical analysis plan.

where, Y_{ij} is viral suppression at 18 months for participant i in cluster j, I_j is the indicator if cluster j is randomized to the MF+ICB arm, S_j is an indicator if cluster j comes from the SOC individuals, VB_{ij} is the baseline viral load for participant i in cluster j, and c_j is the random effect associated with cluster j. The estimator β_1 estimates the difference between the MF+SOC and MF+ICB arms and positive values indicate higher viral suppression in the MF+ICB arm. To test the primary hypothesis we will perform a hypothesis test for H_0 : $\beta_1 = 0$. To test the secondary hypothesis we will perform a hypothesis test for H_0 : $\beta_2 = 0$ and H_0 : $\beta_1 - \beta_2 = 0$.

For the secondary outcomes, we will modify the above model to reflect that retention in care is a proportion and the absolute mean change in systolic blood pressure and HbA1c level are each a continuous outcome. Dropout from the study will be handled using inverse probability weighting.³⁴ The design, analysis, and interpretation of the results from the trial will follow the recommendations given by the CONSORT statement on cluster randomized trials.³⁵ All data will be de-identified prior to the analysis phase.

- 8. Aim 2: Mixed methods to assess mechanisms through which MF and community-based care affect patient outcomes
- 8.1 Study Population and recruitment

For **qualitative mediation analyses**, we will conduct qualitative in-depth with 40 participants from the Aim 1 randomized controlled trial (n=20 from the MF+ICB arm and =20 from the MF+SOC arm). Following the Aim 1 trial's 18-month assessment, research assistants will provide information to a purposively selected sample of n=40 participants and invite them to join the qualitative data collection. Following the Aim 1 trial's 18-month assessment, research assistants will also invite n=10 current AMPATH staff who delivered the intervention to participate in in-depth interviews. Individuals who are interested in participating in the Aim 2 interviews will complete the informed consent form in Appendix V.

- 8.1.1 Inclusion criteria for trial participants:
 - consented to participate in the intervention study (Aim 1) and completed at least the baseline and 18-month assessment;
 - participated in at least 2 MF group meetings during the study period; and
 - able and willing to provide informed consent for the qualitative study.
- 8.1.2 Inclusion criteria for key stakeholder and care providers:
 - Delivered care in the intervention arm of the trial for at least 6 months;
 - 18 years of age or older; and
 - Able and willing to provide informed consent to participate.

Data for all Aim 1 participants (n=900 microfinance groups + 300 SOC) collected via the survey measures (Appendix III) administered at baseline, 9-month, and 18-month follow-up visits will be used for the Aim 2 quantitative mediation analyses.

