- 1.2 18-month viral load will be assessed using blood draws taken during the 18-month assessment in the community (for microfinance group members) and at the facility (for non-microfinance group members).
- 2. For clinical secondary outcomes, we will measure systolic blood pressure and hemoglobin A1c at baseline and 18-months for all 900 microfinance group members enrolled in the trial. Blood pressure will be measured in the community by the clinical officer using a blood pressure arm cuff. HbA1c will be measured in the community by the clinical officers using a point of care test.
- 3. For non-clinical secondary outcomes, we will measure retention in care on an ongoing basis for all enrolled trial participants. Retention in care will be based on study records (REDCap) for intervention recipients and on medical records for facility care patients.
- 4. For exploratory outcomes and mediation analyses, we will collect survey data from all enrolled trial participants: at enrollment and 18-months for all trial participants, with an additional round of survey data collection at month 9 for all microfinance group members. Surveys will be administered by a research assistant to participants in a private location in-person. Surveys will assess demographics, health insurance enrollment and utilization, social support (Oslo Social Support Scale-3), quality of life (adapted version of the MOS-HIV scale), psychological distress (Patient Health Questionnaire-4), self-reported ART adherence (based on the adapted ACTG Adherence Questionnaire), self-reported adherence to NCD medications (based on the extent of DOSE-Nonadherence Questionnaire), barriers to accessing care, patient satisfaction with care, felt HIV stigma (9-item measure of felt stigma validated in Kenya). The survey instrument is included in Appendix III. For exploratory outcomes, we will collect data on microfinance group performance (e.g., saving and lending activities, loan default rates) for all microfinance group participants. Microfinance group performance data will be collected on a quarterly basis and recorded via REDCap. The microfinance data collection tool is included in Appendix IV.

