11. What concerns do you think patients may have about integrating HIV care into microfinance groups?

Probes:

- What do you think they may like about this integrated care model?
- What do you think they may dislike about this integrated care model?

Additional comments

12. Is there anything else that is important for me to understand about community-based care delivery from your perspective? How about microfinance groups? How about the integration of HIV care into microfinance groups?

Closing: Thank participant for their time. Remind participant about the confidentiality of the interview. Ask if they have any questions about anything that was discussed.

EXAMPLE: Thank you for your time and for sharing your thoughts with us. We want to remind you that your comments will remain confidential. Do you have additional questions or comments?

Appendix VIII: NCD screening protocol at study baseline (implemented in all microfinance groups (Study Arms A and B)) **Hypertension (HTN)** Diabetes (DM) Screening Screen for HTN in community groups¹ Screen for DM in community groups (study baseline) FBS < 6.0 mmol/L and FBS \geq 6.1 mmol/L or SBP < 140mmHg SBP ≥ 140mmHg or RBS \leq 7.7 mmol/L RBS \geq 7.8 m/mol/L and DBP < 90mmHg DBP > 90mmHg Perform HbA1C NOW test Discharge Patient needs confirmatory screening in 1 month HbA1C < 6.5 mmol/mol HbA1C ≥ 6.5mmol/mol Counsel on primary prevention; Patient has confirmed DM. begin or continue treatment Discharge Screening (confirmatory 1-month confirmatory screening not required Confirmatory screening for HTN in community group after 1 month) SBP > 140mmHg or SBP < 140mmHg and DBP < 90mmHg DBP > 90mmHg Discharge Patient has confirmed HTN; begin or continue treatment

SBP: systolic blood pressure; DBP: diastolic blood pressure; FBS: fasting blood sugar; RBS: random blood sugar; HbA1C: hemoglobin A1C. Screening for hypertension and diabetes was conducted in the community for all microfinance group members randomized to standard, facilitybased (usual) care and to microfinance group members randomized to the integrated, community-based care intervention.

Addendum to the overall project protocol

This addendum summarizes changes that were made to the overall project protocol after the start of Aim 1 data collection on November 25, 2020.

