- 5. The original project protocol stated that the *primary* endpoint was achievement of HIV viral suppression (HIV-RNA <400 copies/mL) at 18 months. The definition of the primary endpoint was changed such that patients whose 18-month viral load assessment was before January 1, 2023 were considered virologically suppressed if their viral load was <400 copies/mL, and patients whose 18-month viral load assessment was on or after January 1, 2023 were considered suppressed if their viral load was <200 copies/mL. This change to the primary endpoint definition was made to reflect changes to Kenya's national recommendations for HIV monitoring cutoffs that took effect in August 2022 during the active follow-up period.
- 6. The original project protocol stated that blood draws for viral load assessments (primary outcome) would be ascertained for all participants during their 18-month study visit. This protocol was revised such that if a participant had a viral load result available in their medical records within the 3 months prior to their 18-month assessment date, then this result was used to assess their 18-month viral load. This change was made to reduce burden on participants by preventing them from having to provide multiple blood samples within less than 6 months of one another, and to conserve administrative resources and phlebotomist effort.
- 7. The original project protocol stated that the secondary endpoints of (1) absolute mean change in systolic blood pressure and (2) absolute mean change in HbA1c level from 0 to 18 months would be assessed among all enrolled trial participants. This was revised such that the secondary endpoints of (1) absolute mean change in systolic blood pressure and (2) absolute mean change in HbA1c level were only assessed among members of randomized microfinance groups, and were not assessed among matched standard of care patients. This change was made primarily to reduce administrative and logistical burden on the research team. After beginning the matching process, many of the eligible, matched standard of care patients were patients of health facilities that were distinct from those where the majority of microfinance group members received care. For several matched patients, they were the only Harambee participant who was a patient of that health facility. Thus, the human

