- 7. In each county, 10 group leaders from each of the 10 GISHE groups took turns selecting a raffle ticket.
- 8. The group leads then held onto their tickets until all the leads had picked their ticket.
- 9. Once all the leads had a ticket, the leads opened their tickets together and show them to the community attendees.
- 10. The raffle tickets were randomized into the respective Study Arms based on the label as aforementioned in 6a
- 11. Group leads were congratulated and given a chance to ask questions/seek any clarifications

Post Randomization

- 1. Project Manager communicated the randomization outcomes to the larger research team.
- 2. Group representative (group leads) present during the randomization communicated the randomization outcomes to their respective groups.
- 3. Align the Return to Care (RTC) dates for all the Study Arm A members.

10. The original Aim 1 analysis plan for the primary outcome (virologic suppression) that is summarized in section 7.2 of this protocol and in the published protocol ([name] BL et al. Integrated community-based HIV and non-communicable disease care within microfinance groups in Kenya: study protocol for the Harambee cluster randomised trial. BMJ Open. 2021 May 18;11(5):e042662. doi: 10.1136/bmjopen-2020-042662.) was revised. Details of the revised analysis plan, and reasons for the revision(s), are described in the following paragraphs.

Revised Analysis plan

Primary objective: Compare rates of viral suppression between the MF+ICB and MF+UC arms.

Secondary objective 1: Compare rates of viral suppression between the MF+ICB and UC arms.

Secondary objective 2: Compare rates of viral suppression between the MF+UC and UC arms.

Primary outcome definition: Achievement of HIV-1 RNA viral load suppression at 18-months. Participants whose 18-month viral load assessment occurred before January 1, 2023 were considered virologically suppressed if their viral load was <400 copies/mL. To adhere to changes to Kenya's national recommendations for HIV monitoring cutoffs that occurred during the trial, patients whose 18-month viral load assessment was on or after January 1, 2023 were considered suppressed if their viral load was <200 copies/mL.

Analysis set: The analysis set for all objectives is the intent-to-treat set and included all randomized participants for arms MF+ICB and MF+UC and all participants that in the UC arm that provided informed consent.

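### Section 7.2 names no baseline SBP covariate for the SBP-change endpoint; stating one is a nearly free, usually worthwhile gain in precision for a secondary comparison

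*Combined protocol and SAP*

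**What the plan says.** The SBP endpoint is the absolute mean change from 0 to 18 months (Summary; Section 3.4). Its only analysis plan is in Section 7.2. That section writes out a mixed model for viral suppression with an indicator for MF+ICB, an indicator for Arm C, a random cluster effect and one baseline covariate: "VB_{ij} is the baseline viral load for participant i in cluster j". For the secondary outcomes it adds that "we will modify the above model to reflect that retention in care is a proportion and the absolute mean change in systolic blood pressure", together with HbA1c change, is continuous. Outcome type is the only modification stated. On missing follow-up it says "Dropout from the study will be handled using inverse probability weighting".

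The Addendum does not fill the gap:
- Item 7 restricts the SBP and HbA1c endpoints, which "were only assessed among members of randomized microfinance groups, and were not assessed among matched standard of care patients". It gives no model.
- Item 10 revises "The original Aim 1 analysis plan for the primary outcome (virologic suppression) that is summarized in section 7.2 of this protocol". Its covariate lists (county, log baseline viral load, schooling, age, gender, and income in one model) serve viral suppression and contain no SBP.
- Item 11 concerns retention.

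The data needed are planned. Section 7.1, item 2, says "we will measure systolic blood pressure and hemoglobin A1c at baseline and 18-months for all 900 microfinance group members enrolled in the trial". Section 7.1.2 lists "Provide a systolic blood pressure reading (study month 18 only") without the clinical condition that it attaches to HbA1c. The note to Appendix VIII says "Screening for hypertension and diabetes was conducted in the community for all microfinance group members randomized to standard, facilitybased (usual) care", and for the intervention groups too.

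**The concern.** A change score subtracts the whole of a participant's baseline value. Unless baseline and follow-up are very highly correlated, that usually overdoes the correction and adds noise. A model that estimates the baseline slope normally gives a narrower interval from the same data. Baseline viral load, the covariate carried over on a literal reading, does not do this for blood pressure.

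Two things are at stake. The first is the width of the A-versus-B interval for SBP. The second is that, with the covariates unstated, an analyst could choose between an adjusted and an unadjusted estimate after seeing both.

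**Working it through.** **The plan's own figure.** The only power statement (Section 3.4.2) is for viral suppression: above 80% in every scenario. It reproduces. Mean group size after dropout is 22.5 × 0.85 = 19.1, group-size SD is 5 and ICC is 0.05, so the design effect is 1.97 and the effective n per arm is 382.5/1.97 = 194. Power is 91.4% for 20% versus 35%, with a minimum of 84.3% near 42.5% versus 57.5%. There is no figure for SBP to reproduce.

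**Inputs.** The documents give 57 groups randomised (Addendum item 9), at least 40 planned (3.4.1), 900 members, and 15% dropout (3.4.2), which leaves 900 × 0.85 = 765. The following are assumed because the documents do not give them: R, the correlation between group-mean baseline and group-mean month-18 SBP; the SBP SD; the SBP ICC; and k, the ratio of the month-18 to the baseline SD of group means. Baseline viral load is taken to explain none of the SBP variance.

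**Variance, equal spread at both times (k = 1).** With V the variance of a group mean, the change score has variance proportional to 2V(1−R). A model with the participant's own and the group-mean baseline has V(1−R²). The ratio is (1+R)/2, times (J−3)/(J−4) for estimating the group-level slope from J groups.

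| R | ratio, J = 57 | variance falls | interval narrows | variance falls, J = 40 |
|---|---|---|---|---|
| 0.3 | 0.65 × 54/53 = 0.662 | 34% | 19% | 33% |
| 0.5 | 0.75 × 54/53 = 0.764 | 24% | 13% | 23% |
| 0.7 | 0.85 × 54/53 = 0.866 | 13% | 7% | 13% |
| 0.9 | 0.95 × 54/53 = 0.968 | 3% | 2% | 2% |

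The gain is gone at R of about 0.96 (57 groups) or 0.95 (40 groups).

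In mmHg, take an assumed SD of 18, R = 0.5, ICC 0.05 and effective n 194 per arm. The change-score half-width is 1.96 × 18 × √(2 × 0.5) × √(2/194) = 3.6. The adjusted half-width is 3.6 × √0.75 = 3.1, before the small degrees-of-freedom factor.

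**Unequal spread.** The ratio becomes (1−R²)k²/(1+k²−2Rk), times 54/53 for 57 groups.
- R = 0.5, k = 1.2: 0.75 × 1.44/1.24 = 0.871, × 54/53 = 0.887, a fall of 11%.
- R = 0.5, k = 1/1.2: 0.605 × 54/53 = 0.616, a fall of 38%.
- R = 0.7, k = 1.2: 0.966 × 54/53 = 0.985, a fall of about 1.5%. At this k the gain has gone by R of about 0.74.

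**Conditional type I error of the change score (k = 1).** Given a chance baseline difference of c standard errors, its Z statistic has mean −c√((1−R)/2) and variance (1+R)/2. Two-sided rejection at the 5% level:

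| R | c = 0 | c = 1 | c = 2 |
|---|---|---|---|
| 0.3 | 1.5% | 4.6% | 17% |
| 0.5 | 2.4% | 4.8% | 13% |
| 0.7 | 3.4% | 4.9% | 10% |
| 0.9 | 4.4% | 5.0% | 7% |

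Over all randomisations, the variance of Z is (1−R)/2 + (1+R)/2 = 1, so the average is 5%. An imbalance of 2 SE or more has probability 0.046.

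**Why the group mean is needed as well.** A simulation of 82 settings (4,000 replicates each; 765 participants; 57 or 40 groups; group-size SD 5; ICC 0.01 to 0.10) compared the two adjusted models with the change score. With own plus group-mean baseline, the variance ratio was 0.60 to 1.01, within 0.03 of the k = 1 formula throughout, and overall type I error was 3.9% to 6.0%. With own baseline alone, the ratio was 0.63 to 0.97 when within-group and between-group correlations were equal. It reached 1.22 when the group-level correlation was much the higher, exceeding 1 in five settings, all with ICC 0.10 and group-level correlation 0.95. Dropout weighting and county were not simulated.

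**The case against.** The strongest reply is about reading. The model in 7.2 adjusts viral suppression for that outcome's own baseline, so modifying it for SBP may naturally mean replacing baseline viral load with baseline SBP. That is plausible and the text does not exclude it. A reader might infer that the plan rules out baseline adjustment; it does not. But it does not state the swap either, and both readings call for nearly the same added sentence.

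The second reply is about size, and it stands. No SBP correlation, SD or ICC is documented, the ICC of 0.05 belongs to viral suppression, and the simple ratio (1+R)/2 needs equal variances at both times. The 24% at R = 0.5 is therefore one point in a wide range, not an expected saving.

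Third, a reader might take the 17% rejection rate as evidence that the SBP test is invalid. It is not. That figure is conditional on an unusual imbalance and a low correlation, and it is offset by rates below 5% when the arms are balanced.

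Fourth, the Addendum reports completed viral-suppression analyses, so changing the plan may come late. The documents do not say whether SBP has been analysed. This affects how an adjusted result should be labelled, not whether it is informative.

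**Conclusion.** The point holds as a cheap improvement of low severity. Section 7.2 leaves the SBP model without a stated baseline SBP covariate, and the literal analysis would usually be less precise than the planned data allow. With 57 groups and equal variances, the variance reduction from adjustment runs from about 34% at R = 0.3 to 3% at R = 0.9. It shifts materially with the SD ratio and can disappear at high correlation. These figures rest on assumed correlations and variances and leave out weighting and county.

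The documents do not support calling the analysis biased or anticonservative overall, or extending the point to the primary endpoint. HbA1c is left out because its month-18 test is conditional on clinical indication, which raises different questions.

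**What to change.** Add to Section 7.2 a statement that SBP change is compared between Arms A and B only, using a linear mixed model with arm, the participant's baseline SBP in place of baseline viral load, the group-mean baseline SBP and a random group effect, with the dropout weighting already planned. County may be added, since the Summary names it as the stratification factor.

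The cost is one sentence, two covariates in the code and no new data. The group mean uses one group-level degree of freedom, and county would use one more. If SBP has already been analysed, refit once and show the adjusted estimate beside the existing one, labelled as post hoc.
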